8.3. Exploratory Efficacy Analysis

9. Safety and Tolerability Analysis

All safety analyses will be performed on the Safety Population using descriptive statistics. Descriptive summaries by treatment group and overall will be produced. No inferential statistical tests will be performed.

AD-ST-33.06 Effective date: 12-Nov-2020

[figure not shown]

The analysis of safety assessments in this study will include summaries of the following categories of safety and tolerability data collected for each patient:

- Adverse events
 - o TEAEs
 - o SAEs
 - Significant AEs
 - TEAEs leading to discontinuation of IP
 - AEs of Special Interest
 - Positively-adjudicated possible or probable rapidly progressive osteoarthritis (RPOA), subchondral insufficiency fractures, primary osteonecrosis, or pathological fracture
 - Infections that meet SAE and/or severe AE criteria
 - Anaphylactic reactions or infusion-related reactions that lead to permanent discontinuation of administration of IP
 - o TEAEs associated with abnormal liver
 - o Any deaths
 - o Drug induced liver injury

Clinical laboratory investigations

- Vital signs
- Electrocardiograms (ECG)
- COVID-19 screening
- Physical and neurological examination
- Total neuropathy score-nurse
- Motor and sensory nerve conduction studies
- Strength and deep tendon reflexes
- Hypersensitivity /Anaphylactic reactions
- Injection site or infusion reactions
- Liver diagnostic investigations, risk factors, signs and symptoms.
- Infection diagnostic investigations, risk factors, signs and symptoms.
- Prior and concomitant medications and therapies

9.1. Adverse Events

A summary table by treatment group will present the number and percent of subjects reporting:

- Any AEs
- Non-serious AEs occurring in more than 5% of subjects
- Any TEAEs
- Any SAEs
- Any TEAEs possibley related to study drug
- Any TEAEs leading to discontinuation of IP
- Any SAEs possibley related to study drug
- Life-threatenings SAEs
- SAEs resulting in death

Summaries of the incidence of TEAEs will be displayed by treatment group, by ADA status, by severity and by:

- SOC and PT
- SOC, PT, and maximum severity (mild, moderate, severe)
- SOC, PT, and maximum causality (not related, possibly related) to the study drug

[figure not shown]
In the summaries showing severity and relationship to study drug the event with the maximum severity or strongest relationship will be reported. If a particular event is missing the severity and/or relationship, then the strongest possible severity or relationship will be assumed for analysis (severity = severe, relationship = related).

In the case of multiple occurrences of the same AE within the same subject, each subject will only be counted once for each level of summarization.

All AEs will be presented in a by-treatment and by-subject listing, detailing the verbatim term given by the Investigator, the PT, SOC, onset date and time, end date and time, severity, outcome, relationship to study drug, action taken with study drug, other action taken, seriousness, and criteria for seriousness.

9.1.1. Adverse Events Leading to Discontinuation of IP

A summary of incidence rates (frequencies and percentages) of TEAEs leading to discontinuation of IP, by treatment group, SOC, and PT will be prepared. The table will also be produced separately by maximum severity and maximum causality.

A data listing of TEAEs leading to discontinuation of IP will also be provided, displaying details of the event(s) captured on the rCRF.

9.1.2. Deaths and Serious Adverse Events

Any deaths that occur during the study and serious adverse events will be listed.

A summary of incidence rates (frequencies and percentages) of SAEs by treatment group, SOC, and PT will be prepared. The table will also be produced separately for life-threatening SAEs, for SAEs with outcome death and for SAEs by relationship to study medication.

9.1.3. Drug-Induced Liver Injury

A summary of incidence rates of TEAEs associated with abnormal liver by treatment group, SOC, and PT will be prepared.

The type and the results of the liver diagnostic investigation performed will be tabulated by treatment group.

The number and percentage of subjects within each type of liver risk factors and style events will be tabulated by treatment group. Liver signs and symptoms will be presented in the same way.

9.1.4. Infection Risk

A summary of incidence rates of infections that meet SAE or severe AE criteria by treatment group, SOC, and PT will be prepared.

The type and the results of infection diagnostic investigation performed will be tabulated by treatment group.

The number and percentage of subjects within each type of infection risk factors and style events will be tabulated by treatment group. Infection signs and symptoms will be presented in the same way.

9.2. COVID-19 Vaccination and Screening

The number and percentage of fully vaccinated subjects at baseline will be summarized by treatment group.

The symptoms, tests, and results from coronavirus disease 2019 (COVID-19) screening will be tabulated for each visit by treatment group.

[figure not shown]
COVID-19 vaccination, signs, symptoms and impact will be presented in listings.

9.3. Clinical Laboratory Evaluations

Absolute values and changes from baseline will be summarized using descriptive statistics by

AD-ST-33.06 Effective date: 12-Nov-2020

Version 1.1 | Date 31-Aug-2023 | AD-PR-109.02 Effective date: 17-Aug-2020 | Page 33 of 54

treatment group and visit for chemistry, hematology, coagulation, and urinalysis tests.

The number of subjects with clinical laboratory values (chemistry, hematology, coagulation, and urinalysis) categorized as below, within, or above normal ranges (or as either normal or abnormal for urinalysis variables that do not have quantitative ranges) and whether they are clinically significant or not will be tabulated for each clinical laboratory analyte by treatment group and visit. A shift table showing change from baseline in range categories for each clinical laboratory analyte will be produced by treatment group and by visit.

The number of subjects with values for Aspartate aminotransferase (AST) or alanine aminotransferase (ALT) $\geq 3 \times \text{upper limit of normal (ULN)}$, and with values for total bilirubin (TBL) $\geq 2 \times \text{ULN}$ will be summarized in AST, ALT vs. TBL shift tables to identify Potential Hy's Law (PHL) and Hy's Law (HL) cases by treatment group.

Diagnostic immunology, urine pregnancy, and urine drug tests will be presented in by-subject listings only.

All laboratory values will be displayed in the data listings and those that are outside the normal range will be flagged, along with corresponding normal ranges.

9.4. Vital Signs

Descriptive summaries of actual values and changes from baseline by treatment group, visit and time point will be presented for:

- Supine heart rate
- Supine systolic blood pressure
- Supine diastolic blood pressure
- Respiratory rate
- Body temperature
- Standing heart rate
- Standing systolic blood pressure
- Standing diastolic blood pressure

Height, weight, and BMI will be presented at baseline only.

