6.1.8. Derived Variables

- Change from baseline = value at current time point value at baseline.
- Reference End Date = Date of completion/discontinuation.
- Study duration = Reference end date date of first dose of treatment + 1
- Duration of exposure (days) = min(date of last dose of treatment + 14 days or date of death) date of first dose of treatment + 1.
- Treatment-emergent AEs (TEAEs) are defined as:
 - o AEs with onset at the time of or following the start of treatment with IP, or
 - AEs starting prior to the start of treatment but increasing in severity or relationship at the time of, or following, the start of treatment with IP.
- Average Baseline Pain NRS = the arithmetic average of the 'non-missing' daily pain scores within the baseline period defined in Section 6.1.1. For example, if a subject has 5 days of non-missing pain scores their average will be calculated over 5 days, not the full 7-day baseline period.
- Average Week X Pain NRS = the arithmetic average of the 'non-missing' daily pain scores within each subject's specific week X period defined in Section 6.1.5.
- Average Week 12 Pain NRS (LOCF) = the arithmetic average of the 'non-missing' daily pain scores within each subject's specific week 12 period or according to the imputed LOCF/BOCF approach defined in Section 6.1.4.
- Change from Baseline to Week X Pain NRS = for each subject 'Average Week X Pain NRS' minus 'Average Baseline Pain NRS'.
- Change from Baseline to Week 12 Pain NRS (LOCF/BOCF) = for each subject 'Average Week 12 Pain NRS (LOCF)' minus 'Average Baseline Pain NRS'.
- Galer NPS Total Score (ranges from 0 to 100): sum of Pain Intensity, Pain Unpleasantness, Pain Sharpness, Pain Hotness, Pain Dullness, Pain Coldness, Pain Sensitivity, Pain Itching, Deep Pain Intensity, and Surface Pain Intensity (All in an 11-point NRS).
- Change from Baseline to Week X Galer NPS Total Score = for each subject 'Galer NPS Total Score' minus 'Baseline Galer NPS Total Score'.
- Total number of days rescue medication was used = End Date of Medication Start Date

of medication + 1. Each day on which rescue medication was used at least once is counted.

- Cumulative consumption (mg) of paracetamol rescue medication use = Total dose of rescue medication (mg) consumed during the days in which paracetamol was used.

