9.7. Total Neuropathy Score-Nurse

Descriptive summaries of the TNSn will be presented by treatment groups and by visit. Additionally, the number and percentage of subjects within each category (0, 1, 2, 3, and 4) for each sub-score (sensory symptom, motor symptom, autonomic symptom, pin sensibility, vibration sensibility) will be summarized by treatment group and by visit.

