6.5. Other Safety Data

[figure not shown]
Table 14.3.5.1
Descriptive Summary of Vital Signs
Safety Population

	Placebo		MEDI7352			Total
Visit		CCI	CCI	CCI	All MEDI7352	
Statistic	(N=xx)	(N=xx)	(N=xx)	(N=xx)	(N=xx)	(N=xx)
Baseline [1]						
n	XX	XX	XX	XX	XX	XX
Mean (SD)	xx.x (xx.xx)	xx.x(xx.xx)	xx.x(xx.xx)	xx.x(xx.xx)	xx.x(xx.xx)	xx.x (xx.xx)
Median	XX.X	XX.X	XX.X	XX.X	XX.X	XX.X
Q1, Q3	XX.X, XX.X	XX.X, XX.X	XX.X, XX.X	XX.X, XX.X	XX.X, XX.X	XX.X, XX.X
Min, Max	XX, XX	xx, xx	xx, xx	XX, XX	xx, xx	XX, XX
Day 1: 15 Minutes Post- Dose						
n	XX	XX	XX	XX	XX	XX
Mean (SD)	xx.x(xx.xx)	xx.x(xx.xx)	xx.x(xx.xx)	xx.x(xx.xx)	xx.x(xx.xx)	xx.x (xx.xx)
Median	XX.X	XX.X	XX.X	XX.X	XX.X	XX.X
Q1, Q3	XX.X, XX.X	XX.X, XX.X	XX.X, XX.X	XX.X, XX.X	XX.X, XX.X	XX.X, XX.X
Min, Max	XX, XX	xx, xx	xx, xx	XX, XX	xx, xx	xx, xx
Day 1: 15 Minutes Post-						
Dose CFB						
n	XX	XX	XX	XX	XX	XX
Mean (SD)	xx.x(xx.xx)	xx.x(xx.xx)	xx.x(xx.xx)	xx.x(xx.xx)	xx.x(xx.xx)	xx.x (xx.xx)
Median	XX.X	XX.X	XX.X	XX.X	XX.X	XX.X
Q1, Q3	XX.X, XX.X	XX.X, XX.X	XX.X, XX.X	XX.X, XX.X	XX.X, XX.X	XX.X, XX.X
Min, Max	XX, XX	XX, XX	XX, XX	XX, XX	XX, XX	XX, XX

^{• • • •}

CFB = Change from Baseline; n = number of subjects by treatment group at each visit for the parameter; N = number of subjects per treatment group; SD = standard deviation; Q1 = first quartile; Q3 = third quartile.

^[1] Baseline is defined as the last observation recorded prior to the first dose of treatment. Reference Listing: 16.2.9.1

Programming Notes:

- Repeat for Supine Heart Rate, Supine Systolic Blood Pressure, Supine Diastolic Blood Pressure, Respiratory Rate, Body Temperature, Standing Heart Rate, Standing Systolic Blood Pressure, Standing Diastolic Blood Pressure.
- After Week 2 (inclusive), Supine measure are taken in sitting position. We will consider them as supine (in resting position) for calculating Change from Baseline (always at supine position).

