- Include the following timepoints: Baseline, Day 1: 5 Minutes Post-Dose, Day 1: 15 Minutes Post-Dose, Day 1: 30 Minutes Post-Dose, Day 1: 45 Minutes Post-Dose, Day 1: 1 hour Post-Dose, Day 1: 2 hours Post-Dose, Day 1: 4 hours Post-Dose, Week 2: Pre-Dose, Week 2: 5 minutes after Infusion Completion, Week 4: Pre-Dose, Week 4: 5 minutes after Infusion Completion, Week 6: Pre-Dose, Week 6: 5 minutes after Infusion Completion, Week 8: Pre-Dose, Week 8: 5 minutes after Infusion Completion, Week 10: Pre-Dose, Week 10: 5 minutes after Infusion Completion, Week 11, Week 12, Week 18. (Do not include Screening records).
- Note that Body To, and standing measures are not taken on Day 1, at 15, 30 and 45 minutes post-dose.
- A column for dosing (c) will only be added if Stage 4 is initiated.

Final 1.0 | 12-Jul-2023 | Page 88 of 205

[figure not shown]

Table 14.3.5.2 Descriptive Summary of ECG Data Safety Population

Parameter: xxxxx

[figure not shown]
	Placebo		MEDI7352			Total
Visit/		CCI	CCI	CCI	All MEDI7352	
Statistic	(N=xx)	(N=xx)	(N=xx)	(N=xx)	(N=xx)	(N=xx)
Baseline [1]						
n	XX	XX	XX	XX	XX	XX
Mean (SD)	xx.x (xx.xx)	xx.x(xx.xx)	xx.x(xx.xx)	xx.x (xx.xx)	xx.x(xx.xx)	xx.x (xx.xx)
Median	XX.X	XX.X	XX.X	XX.X	XX.X	xx.x
Q1, Q3	XX.X, XX.X	XX.X, XX.X	XX.X, XX.X	XX.X, XX.X	XX.X, XX.X	XX.X, XX.X
Min, Max	xx, xx	xx, xx	xx, xx	xx, xx	xx, xx	xx, xx
Day 1: 1 hour Post-Dose						
n	XX	XX	XX	XX	XX	XX
Mean (SD)	xx.x (xx.xx)	xx.x(xx.xx)	xx.x(xx.xx)	xx.x (xx.xx)	xx.x (xx.xx)	xx.x (xx.xx)
Median	XX.X	XX.X	XX.X	XX.X	XX.X	XX.X
Q1, Q3	XX.X, XX.X	XX.X, XX.X	XX.X, XX.X	XX.X, XX.X	XX.X, XX.X	XX.X, XX.X
Min, Max	xx, xx	xx, xx	xx, xx	xx, xx	XX, XX	XX, XX
Day 1: 1 hour Post-Dose						
CFB						
n	XX	XX	XX	XX	XX	XX
Mean (SD)	xx.x(xx.xx)	xx.x(xx.xx)	xx.x(xx.xx)	xx.x (xx.xx)	xx.x(xx.xx)	xx.x (xx.xx)
Median	XX.X	XX.X	XX.X	XX.X	XX.X	XX.X
Q1, Q3	XX.X, XX.X	XX.X, XX.X	XX.X, XX.X	XX.X, XX.X	XX.X, XX.X	xx.x, xx.x
Min, Max	XX, XX	XX, XX	XX, XX	XX, XX	XX, XX	XX, XX

CFB = Change from Baseline; n = number of subjects by treatment group at each visit for the parameter; N = number of subjects per treatment group; SD = standard deviation; Q1 = first quartile; Q3 = third quartile.

Note: Data shown are averages of the 3 replicates taken for each parameter and timepoint, and CFB for the same variables.

[1] Baseline is defined as the last observation recorded prior to the first dose of treatment.

Reference Listing: 16.2.9.2

Programming Notes:

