- Study Visit in x axis and Systolic Blood Pressure (mmHg) in y axis.
- Include a profile for Resting SBP and another for Standing SBP.
- Include the following timepoints: Baseline, Day 1: 15 Minutes Post-Dose, Day 1: 30 Minutes Post-Dose, Day 1: 45 Minutes Post-Dose, Day 1: 1 hour Post-Dose, Day 1: 2 hours Post-Dose, Day 1: 4 hours Post-Dose, Week 2: Pre-Dose, Week 2: 5 minutes after Infusion Completion, Week 4: Pre-Dose, Week 4: 5 minutes after Infusion Completion, Week 6: Pre-Dose, Week 6: 5 minutes after Infusion Completion, Week 8: Pre-Dose, Week 8: 5 minutes after Infusion Completion, Week 10: Pre-Dose, Week 10: 5 minutes after Infusion Completion, Week 11, Week 12, Week 18. (Do not include Screening records).
- Note that standing measures are not taken on Day 1, at 15, 30 and 45 minutes post-dose.
- Make one plot for each dose treatment group, for a total of 4 plots with two profiles each.
- A plot for column dosing (column dosing will only be added if Stage 4 is initiated.

Final 1.0 | 12-Jul-2023 | Page 195 of 205

[figure not shown]

Figure 14.3.6.1.2 Vital Sign Profiles: Mean (±SD) Diastolic Blood Pressure over time Safety Population

1H PD = 1 Hour Post-Dose; 15M PD = 15 Minutes Post-Dose; 2H PD = 2 Hours Post-Dose; 30M PD = 30 Minutes Post-Dose; 4H PD = 4 hours Post-Dose; 45M PD = 45 Minutes Post-Dose; 5M PD = 5 minutes after Infusion Completion; BASE = Baseline; D1 = Day 1; DBP = Diastolic Blood Pressure; W2 = Week 2; W4 = Week 4; W6 = Week 6; W8 = Week 8; W10 = Week 10; W11 = Week 11; W12 = Week 12; W18 = Week 18.

Baseline is defined as the last observation recorded prior to the first dose of treatment.

Safety Population = includes all subjects who receive at least 1 dose of double-blind study medication.

Reference Listing: 16.2.9.1

Programming Notes:

- Same shell as Figure 14.2.1.4
- Insert the following text as legend: "Average DBP ± Standard Deviation".
- Study Visit in x axis and Diastolic Blood Pressure (mmHg) in y axis.
- Include a profile for Resting DBP and another for Standing DBP.

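### No paired resting-to-standing change in blood pressure or heart rate is derived, summarised or counted, and from Week 2 sitting readings are treated as supine

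*SAP*

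**What the plan says.** Section 9.4 of SAP v1.1 opens with "Descriptive summaries of actual values and changes from baseline by treatment group, visit and time point will be presented for" and then lists eight parameters. Supine heart rate, systolic and diastolic pressure are three of them, and the standing versions, such as "Standing systolic blood pressure", are three more. The general change variable in section 6.1.8 runs over time within one parameter: "Change from baseline = value at current time point value at baseline" (the minus sign is lost in the text). No difference between postures is defined there.

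The version 1.0 shell for Table 14.3.5.1 keeps the same structure: "Repeat for Supine Heart Rate, Supine Systolic Blood Pressure, Supine Diastolic Blood Pressure, Respiratory Rate, Body Temperature, Standing Heart Rate, Standing Systolic Blood Pressure", with standing diastolic pressure completing the list. It gives n, mean, SD, median, quartiles, minimum and maximum, for values and for change from baseline. The notes to Figure 14.3.6.1.1 say "Include a profile for Resting SBP and another for Standing SBP", and the diastolic and heart-rate figures follow the same pattern.

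Two further shell notes matter. From Week 2 the resting reading is taken sitting, and the note adds: "We will consider them as supine (in resting position) for calculating Change from Baseline (always at supine position". The shell also states that "standing measures are not taken on Day 1, at 15, 30 and 45 minutes post-dose".

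**The concern.** Section 2.2.2 names vital signs as a safety endpoint. The subjects have diabetic neuropathy, and section 9.7 already tabulates a neuropathy score whose components include "autonomic symptom, pin sensibility, vibration sensibility". A drug effect on postural control would show as more subjects whose pressure drops when they stand. That is a difference between two readings in the same person, and two separate marginal distributions cannot recover it. The trial collects both readings, yet no summary output would show such a signal. Elsewhere in section 9 subject-level counts are planned: range categories and shift tables for laboratory values (9.3) and normal or abnormal counts for ECGs (9.5). Vital signs have none.

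The posture switch adds a second problem. A change from a supine baseline to a sitting Week 2 value, both labelled supine, contains a posture effect as well as any change over time. The gap between the resting and standing profiles in the figures also changes meaning at Week 2.

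**Working it through.** The plan states no figure on this point, so there is none to reproduce. The check has two parts.

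**1. Reading the outputs together**

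| Place | What it provides | Paired difference or count? |
|---|---|---|
| SAP v1.1, 9.4 | Value and change from baseline, each posture separate | No |
| SAP v1.1, 6.1.8 | Change over time within a parameter | No |
| Table 14.3.5.1 (shell v1.0) | Eight parameters with full descriptive statistics | No |
| Figures 14.3.6.1.1 to 14.3.6.1.3 | Mean ± SD, resting and standing profiles | No |
| Listing 16.2.9.1 (shell v1.0) | Both postures per subject, with position shown | Not paired, no flag |

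The listing is sorted by arm, subject, parameter and date, so resting and standing systolic readings fall in different blocks. Its schedule has 21 timepoints. Removing screening and the three Day 1 times without standing readings leaves 17. If both postures were taken at all 17, the 272 planned subjects would give 272 × 17 = 4,624 systolic pairs to match by hand. Stages 1 to 3 alone (10 + 30 + 67 = 107 subjects) would give 107 × 17 = 1,819.

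**2. How visible a few falls would be (illustration)**

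Inputs from the SAP: planned evaluable numbers on active doses of 37, 51 and 67 (section 3.2). These are efficacy counts with stage 4 included, used here only for scale.

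Assumed inputs, not in the documents: supine systolic pressure with mean 135 and SD 15; ordinary fall on standing with mean 3 and SD 8; k subjects with an additional fall F; a 20 mmHg cut-off used only to illustrate a count.

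Shift in mean standing pressure = k × F / n:

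- k = 3, F = 30: 90/37 = 2.4, 90/51 = 1.8, 90/67 = 1.3 mmHg.
- k = 2, F = 20: 40/37 = 1.1, 40/51 = 0.8, 40/67 = 0.6 mmHg.

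Standard deviation of standing pressure without added fallers: √(15² + 8²) = 17.0 (16.9 simulated). The standard error is about 2.4 at n = 51 and 2.1 at n = 67, larger than the corresponding shifts of 1.8 and 1.3. With three 30 mmHg fallers the simulated SD rises only to about 18.4 (n = 51) or 18.1 (n = 67).

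Count of paired falls of 20 mmHg or more. Background probability: P(N(3, 8) ≥ 20) = 1 − Φ(2.125) = 0.017. For a subject with the extra 30 mmHg: P(N(33, 8) ≥ 20) = Φ(1.625) = 0.95.

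- n = 51: from 51 × 0.0168 = 0.9 to 48 × 0.0168 + 3 × 0.948 = 3.7.
- n = 67: from 67 × 0.0168 = 1.1 to 64 × 0.0168 + 3 × 0.948 = 3.9.

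Simulation gives the same values. The count moves where the mean does not, but it does not start from zero, so it needs the placebo arm beside it.

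**The case against.** A reader might infer that the plan reports only group means, or that postural falls are never reported. The documents do not support either. The table shell also has SD, median, quartiles, minimum and maximum; Listing 16.2.9.1 carries every subject's readings in both postures; and a postural event reported as an adverse event would enter the adverse event tables. These safeguards are partial. The minimum is one value, and it does not show a fall from that subject's own resting reading. In the simulation, with two or three fallers of 20 to 40 mmHg at n = 51 or 67, the lowest standing value belonged to a faller in about 26% to 87% of groups. The minimum change from baseline in standing pressure mixes a postural fall with a general one. Adverse event tables do not capture asymptomatic measured falls.

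It is also fair to say that no objective, endpoint or event of special interest in the SAP names postural change, that safety analysis is descriptive, and that the protocol, which is not shown, may deal with orthostatic assessment. That makes this an improvement and not a contradiction. The vital-signs shells are available only in version 1.0; SAP v1.1 keeps the same parameters and the same table, figure and listing titles, so the reading probably carries over but cannot be confirmed.

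The strongest practical objection is the posture switch: Day 1 differences are supine to standing and later ones sitting to standing, so the later differences have no like-for-like baseline. This stands, and it limits the fix to comparing arms within a visit.

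**Conclusion.** The point holds in limited form. No within-subject postural change is derived, summarised or counted in section 9.4, the derived variables, Table 14.3.5.1 or the figures. It can be recovered only by matching separate parameter blocks in the listing. Change from baseline in the values labelled supine also mixes postures from Week 2. A few large falls on one dose could pass unnoticed in the summaries: on the assumed values, a mean shift of 1.3 to 2.4 mmHg for three falls of 30 mmHg. The blood pressure figures are illustrative and say nothing about whether the drug has such an effect. The point is minor: it concerns how collected safety data are displayed and affects no efficacy conclusion.

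**What to change.** In section 9.4 and Table 14.3.5.1:

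- Derive standing minus resting systolic pressure, diastolic pressure and heart rate at each timepoint where both are measured.
- Label the resting posture as supine on Day 1 and sitting from Week 2, and summarise the difference by arm within visit.
- Do not compute change from baseline across different resting postures, or label it clearly if it is kept. This applies to the existing supine parameters too.
- Add the number of subjects with any post-baseline fall beyond a threshold that the sponsor fixes before unblinding. Report supine-to-standing and sitting-to-standing separately, with placebo alongside because background falls are expected.
- Flag those subjects in Listing 16.2.9.1.

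The cost is three derived differences, posture labels, a few table rows and a listing flag: some programming and slightly longer safety output, with no new data collection.
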